| combined | 21 | 6 | 0.7121396 | 3.263434 | 4.514503 7.485497 |
| diff | -3 | 1.38873 | | -5.906646 | -0.0933544 |
| Diff= mean (x) – mean (y) | | | | t = -2.1602 | |
| Ho: diff = 0 | | | | Degrees of freedom = 19 | |
| Ha: diff < 0 | | Ha: diff != 0 | | Ha: diff > 0 | |
| Pr(T < t) = 0.0219 | | Pr(T > t) = 0.0437 | | Pr(T > t) = 0.9781 | |

Statistical plan for analyzing at least the primary hypothesis:

The sample size is powered to detect small differences in NRS score. Because itch is subjective and varies daily, subjects will be asked to keep an itch diary every day. For each subject, we will plot their average itch scores over time before and after drug intervention. For each dosage group, we will use linear regression methods with mix effects (GLM, SAS) to track the change in itch in each of the groups from baseline. This study will provide the effect size, standard deviation and range of itch scores in EB patients in order to properly power a larger phase 2 trial. This study can detect large differences in itch scores should Serlopitant decrease itch from severe to low-none at 1 and 2 months. At the 3 month follow up, we will measure the durability and length of response.

Matrix showing procedure plan for each study visit:

| Schedule of Events for Phase 2 Serlopitant | | | | | | | |
|--|------------------|-----------------|------------------------------|----------------|----------------|----------------|----------------|
| | Screening period | | Treatment period | | | Follow up | |
| | Phone call | Visit 1 | | Visit 2 | Visit 3 | Phone call | Early Term |
| | Screening call | Screening visit | Determination of Eligibility | Month 1 | Month 2/EOT | Month 3 | |
| Examination | Day -60 to -30 | Day -44* to -1 | Months 6 to 0 | Day 30 ±14 | Day 60 ±14 | Day 90 ±14 | |
| Informed consent/ Photographic consent | | X | | | | | |
| Demographics | | X | | | | | |
| Medical history | | X | Review | | | | |
| Prior ^a & current medications | X | X | | X | X | X | X |
| Abbreviated physical examination | | X | | | X | | X |
| Vital signs | | X | | X | X | | X |
| Urine pregnancy test (UPT) ^b | | X | Review results | X | X | | X |
| Inclusion/exclusion criteria | X | X | | | | | |
| Blood samples for clinical laboratory tests ^c | | X ^c | Review results | X ^c | X ^c | | X ^c |
| Randomization | | | X ^h | | | | |
| NRS ^d & Stanford EB survey | | X | | X | X | X ^e | X |
| Photograph the affected area ^f | | X | | X | X | | X |

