| Dispense study medication | | | X ^h | X | | | |
| Dispense subject diary | | X | X ^h | X | X ^g | | |
| Review/collect diary with subject | | | | X | X | X | X |
| Review and record adverse events | | | | X | X | X | X |

Note: NRS = numeric rating score.

* Includes up to 30 day washout from prohibited medications. The study medication and diary dispensation are to occur no more than 1-2 weeks after Screening Visit.

- a: all medications taken within 30 days prior to screening.
- b: for females of child-bearing potential.
- c: all subjects: hematology, serum chemistry will be measured at Screening, Month 1, and Month 2/EOT or early termination (ET).
- d: NRS recorded by subject daily, using diary, from screening visit through the end of the study; NRS is included in the Stanford EB Itch survey.
- e: the Stanford EB survey will be administered over the phone by a member of the research staff.
- f: photographs taken only if patient has signed photography consent
- g: a return envelope will be provided for the patient to return the study diary to Stanford after the follow up phone call

| | Schedule of Events for Phase 2 Serlopitant | | | | | | |
|--|--|---------|------------------|---------|---------|------------|------------|
| | Screening period | | Treatment period | | | Follow up | |
| | Phone call | Visit 1 | | Visit 2 | Visit 3 | Phone call | Early Term |

h: Patient letter of enrollment and study medication will be mailed to patient after determination of eligibility following the Screening Visit

Each subject will be un-blinded individually after completing 3 months of study period. All patients who complete the study will be offered a 2-month trial on active drug. Patient who received active drug in the first phase will be contacted and asked if they would like to continue on active drug for an additional 2 months. Patients who received placebo in the first phase will be contacted and asked if they would like to repeat the study on open label for 2 months.

When this occurs, the schedule of events will be as follows:

Patients who would like to continue with the treatment for the open-label extension portion of the study will be provided with the research medication and research daily diary. They will be followed up by phone at baseline, 1 month, 2 months, and 3 months (wash out). In addition, they will go to an external lab near their home for lab monitoring that will occur once a month for the two months they are on active drug.

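### A subject may be told the treatment arm while still holding the follow-up diary, because unblinding does not wait for the Month 3 call or for the diary's return

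*Combined protocol and SAP*

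**What the plan says.** All the relevant text is in section 8 of the combined protocol and SAP.

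- Schedule of Events, footnote d, on who scores itch and for how long: "NRS recorded by subject daily, using diary, from screening visit through the end of the study; NRS is included in the Stanford EB Itch survey".
- Footnote g, attached to the diary dispensed at Month 2: "a return envelope will be provided for the patient to return the study diary to Stanford after the follow up phone call". No return deadline is given.
- Footnote e, on the Month 3 contact: "the Stanford EB survey will be administered over the phone by a member of the research staff".
- The schedule row for diary handling, marked at Months 1, 2 and 3 and at early termination: "Review/collect diary with subject | | | | X | X | X | X". The Month 3 column is a phone call, at Day 90 ±14.
- Text after the schedule, on unblinding: "Each subject will be un-blinded individually after completing 3 months of study period".
- The same paragraph offers every completer two months of active drug, but words the approach by arm. For example: "Patients who received placebo in the first phase will be contacted and asked if they would like to repeat the study on open label for" two months.
- Statistical plan, on the use of the Month 3 data: "At the 3 month follow up, we will measure the durability and length of response".

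**The concern.** The subject is the outcome assessor for the itch score, so the blind that matters most for the diary is the subject's own. The last diary covers the period after treatment ends and is returned by post, which makes it a physical record that stays in the subject's hands until mailed. The unblinding rule is tied to time in the study, not to the arrival of that record. A subject who has learned the arm, either by being told or from the way the extension is offered, could fill in missed days, alter entries or not send the diary back. Any of these could be coloured by knowing the arm. What is at stake is the Month 3 assessment of whether and for how long a response persists off drug.

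**Working it through.** No figure in the plan bears on this point, and the sample-size table is not involved. The check is to put the events in order.

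**Inputs (Schedule of Events)**
- Month 2 visit: Day 60 ±14, so Day 60 − 14 = 46 to Day 60 + 14 = 74.
- Month 3 call: Day 90 ±14, so Day 90 − 14 = 76 to Day 90 + 14 = 104.
- Diary posted: after the call, with no latest date.
- Unblinding: after three months, per subject. The plan does not define this as Day 90, as completion of the call, or as receipt of the diary.

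**Length of the follow-up diary**
- Nominal: 90 − 60 = 30 days.
- Within the windows: from 76 − 74 = 2 days to 104 − 46 = 58 days.

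**Reading A: three months means Day 90**
- The call may fall up to 104 − 90 = 14 days after the code could be broken.
- In that interval the subject could still be making diary entries, and would then answer the phone survey, knowing the arm.
- If the call falls on or before Day 90, the survey is blinded, but the diary may still be unposted when the code is broken.

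**Reading B: three months means the call has been completed**
- The phone survey is then taken before unblinding.
- The diary is still with the subject, because footnote g has it posted after the call. The exposed interval runs from unblinding until posting, and its length is not specified.

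**Reading C: three months includes return of the diary**
- There would be no gap, but the plan does not say this.

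**Other safeguards in the text**
- Month 1 and Month 2 diaries: review or collection is scheduled at visits, before the stated point of unblinding.
- Month 3 diary: the same row is marked, but the contact is by phone. The diary can be discussed then but not handed over, and the plan does not say that scores are transcribed during the call.
- Month 3 survey: taken by staff by phone and includes an NRS, so it does not depend on the posted diary.

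Readings A and B both leave the diary unprotected for some period. Only Reading C, which is unstated, closes the gap.

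**The case against.** The strongest reply is that the plan has more protection than footnote g alone suggests. The diary is due for review with the subject at the Month 3 call, so entries discussed with staff would be harder to backfill or change unnoticed. The phone survey supplies a separate NRS at the same time point. Completing three months can naturally be read as completing the Month 3 procedures, which would leave only the interval between call and posting. The main comparison is placed earlier: "This study can detect large differences in itch scores should Serlopitant decrease itch from severe to low-none at 1 and 2 months".

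Most of this stands, and it limits the point to Month 3. It does not remove it. A phone review does not stop later edits or non-return. One phone score cannot replace a daily series for judging the length of a response. The survey is blinded only if the call comes before unblinding, which the plan does not guarantee.

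Two stronger readings are tempting, and the documents support neither.

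- A reader might infer that diaries would go missing at different rates in the two arms once the extension is offered. The plan offers all completers active drug for two months, so a difference between arms in the incentive to withhold a diary is not shown.
- A reader might want to express the bias in NRS points. That needs the share of days entered or changed after unblinding and the size and direction of the shift in each arm. The plan gives none of these, and not every follow-up diary day should be counted as exposed, since most should already be recorded and reviewed by the time of the call.

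**Conclusion.** The point holds as a gap in sequence. The plan allows a self-assessing subject to know the arm while the follow-up diary is unreturned and, on the Day 90 reading, up to 14 days before the Month 3 call. It does not show that this will happen to every subject, or that entries will in fact be altered.

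The exposure is limited to the Month 3 data on durability and duration of response. The Month 1 and Month 2 comparisons are largely untouched, and no sample size or power figure changes. The size of any bias cannot be estimated from the documents.

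The conclusion rests on two assumptions: that earlier diaries are collected at the visits as the schedule suggests, and that the main comparison is at 1 and 2 months. The plan does not say whether follow-up diary days enter the mixed-effects regression. It is worth correcting because the remedy is cheap and protects data that the plan intends to use.

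**What to change.** Replace the unblinding sentence with a rule on order: a subject's code is broken, and the arm-specific extension contact is made, only after (1) the Month 3 call and Stanford EB survey are done and (2) the last diary has been received and entered, or recorded as lost after a stated number of reminders. Add a matching cross-reference to footnote g.

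The rule can be combined with any rule that keeps staff and analysts blinded. The change is one sentence, with no new data collection and no change in sample size. The downside is that the extension offer waits for the post.

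### Each subject's code is broken after that subject's own Month 3, and nothing keeps those who assess or analyse later subjects from knowing it

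*Combined protocol and SAP*

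**What the plan says.** The text after the Schedule of Events in section 8 of the combined protocol and SAP sets the rule: "Each subject will be un-blinded individually after completing 3 months of study period". The open-label extension is open to everyone: "All patients who complete the study will be offered a 2-month trial on active drug". The approach nevertheless differs by arm. For one arm, "Patient who received active drug in the first phase will be contacted and asked if they would like to continue on active drug"; for the other, "Patients who received placebo in the first phase will be contacted and asked if they would like to repeat the study on open label".

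Some assessment work falls at or after the time when codes are being broken:

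- **Month 3 survey.** Schedule of Events, footnote e: "the Stanford EB survey will be administered over the phone by a member of the research staff". The statistical plan uses this contact: "At the 3 month follow up, we will measure the durability and length of response".
- **Last diary.** Footnote g: "a return envelope will be provided for the patient to return the study diary to Stanford after the follow up phone call".
- **Adverse events.** The schedule has AEs reviewed at Months 1, 2 and 3. The Data Monitoring Plan gives oversight and judgement to the principal investigator, without a data safety monitoring board.
- **Photographs.** Section 5 makes wound healing from serial photographs a secondary aim. The reader and the time of reading are not stated.
- **Analysis.** Section 8, statistical plan: "we will use linear regression methods with mix effects (GLM, SAS) to track the change in itch in each of the groups from baseline".

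The only other mention of blinding is in section 6, about an earlier trial.

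**The concern.** Staff who contact completers by arm must know the arm. They also know how those completers fared. Nothing stops the same people from interviewing, judging AEs, reading photographs or analysing for subjects who entered later.

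Knowing which completers had active drug, and how they did, can shape a phone interview, a causality judgement or a wound reading. It can also shape the choice of analysis. Sections 5 and 8 state a comparison with placebo and a two-sample power basis, but the analysis paragraph describes only change within each group. The exact between-arm contrast could therefore be settled after arm results are known. Section 8 says that this trial is to supply the effect size and standard deviation for a larger one, so a contrast chosen that way would carry over into later planning.

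The last diary adds a smaller gap. It is posted after the Month 3 call, and the text does not make the code break wait for it.

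**Working it through.** The plan gives no figure on this point to reproduce. I compared the timing rules, then counted how many contacts could fall after codes are known.

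**Inputs from the plan.** Nominal visits are Day 30, 60 and 90, each ±14 days (Schedule of Events). The code break comes after the subject's own 3 months; no interval is given. The sample size section gives both 14 patients in total and 7 + 14 = 21, so both are shown.

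**Assumptions, because the plan is silent.** Subject i (i = 0 to N−1) enters on day e_i = 30A × i/(N−1), which is even entry over A months of 30 days. The code is broken on day e_i + 90 + L, with lag L = 0 or 14 days. A contact counts as exposed if it falls strictly after the trigger. The trigger is the first code break (day 90 + L), or the break at which half of the codes are known (the 7th of 14 or the 11th of 21).

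**Formulae for the first-break trigger.** A Month 3 call is exposed if e_i > L. A Month 2 visit is exposed if e_i > 30 + L. A Month 1 visit is exposed if e_i > 60 + L.

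**Worked case: N = 14, A = 3.** Spacing is 90/13 = 6.92 days.

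- L = 0. Month 3: i ≥ 1, so 13. Month 2: i > 30/6.92 = 4.33, so i = 5 to 13, which is 9. Month 1: i > 60/6.92 = 8.67, so i = 9 to 13, which is 5. Months 1 and 2 together: 14 of 28.
- L = 14. Month 3: i > 14/6.92 = 2.02, so i = 3 to 13, which is 11. Month 2: i > 44/6.92 = 6.36, which gives 7. Month 1: i > 74/6.92 = 10.69, which gives 3. Months 1 and 2 together: 10 of 28.

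**All cases** (entry over 1, 3, 6, 12 months):

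| Contacts after the trigger | Lag | N = 14 | N = 21 |
|---|---|---|---|
| Month 3, first code | 0 | 13, 13, 13, 13 of 14 | 20, 20, 20, 20 of 21 |
| Month 3, first code | 14 days | 7, 11, 12, 13 of 14 | 11, 17, 19, 20 of 21 |
| Month 3, half of codes | 0 | 7, 7, 7, 7 of 14 | 10, 10, 10, 10 of 21 |
| Month 3, half of codes | 14 days | 1, 5, 6, 7 of 14 | 1, 7, 9, 10 of 21 |
| Months 1 + 2, first code | 0 | 0, 14, 20, 23 of 28 | 0, 21, 31, 36 of 42 |
| Months 1 + 2, first code | 14 days | 0, 10, 18, 23 of 28 | 0, 15, 28, 34 of 42 |
| Months 1 + 2, half of codes | 0 | 0, 3, 8, 11 of 28 | 0, 4, 11, 16 of 42 |
| Months 1 + 2, half of codes | 14 days | 0, 1, 6, 11 of 28 | 0, 1, 8, 14 of 42 |

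The Month 3 figure of N−1 at zero lag follows directly from the assumption: every later entrant's call comes after the first break. Simultaneous entry would not remove the overlap entirely, because the visit window lets Month 3 calls for same-day entrants fall 104 − 76 = 28 days apart.

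**What each contact involves.** Month 3 calls carry a staff-run survey and AE review. Months 1 and 2 carry AE and diary review; the plan does not say that staff administer the survey then.

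**The case against.** The strongest reply is that the main evidence is hardly touched. Efficacy rests on patient self-report. Each subject records the daily diary, and answers even the Month 3 survey, before that subject's own code is broken. Telling subjects their arm before an extension is a deliberate and disclosed choice. This stands, and it limits the weight of the point.

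Other parts of the reply also stand:

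- A reader might infer that early code breaks reveal the arms of subjects still in the trial. The documents do not support that. One known code discloses another only if allocation can be inferred, for example from small blocks or shared kit codes. The randomisation method is not described, so this is neither shown nor excluded.
- A reader might infer that site staff read the photographs and choose the analysis. The text assigns neither task. The documented staff roles are the Month 3 phone survey and AE review. For the other two, the gap is that nothing protects whoever does them.
- A reader might infer that no comparison with placebo is planned. Sections 5 and 8 do state one. What is missing is the exact contrast in the analysis paragraph. That is a separate weakness which unblinding did not cause; it matters here only because it leaves a choice open when codes become known.
- The counts depend on an accrual pattern that the plan does not give, and a lag lowers most of them.

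What does not stand is that silence on procedure makes this only a reporting matter. The plan states a rule of individual code breaks and arm-specific contacts. If entry is staggered, following that rule as written lets arm results build up before follow-up, photograph reading and analysis are finished.

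**Conclusion.** The point holds as a limited one that is cheap to correct. If entry is staggered, the plan as written permits people who know completed subjects' arms and outcomes to run later Month 3 surveys and review later AEs. It leaves the photograph reader and the analyst unprotected too.

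The possible exposure at Month 3 ranges from 7 of 14 (11 of 21) calls, with entry over one month and a 14-day lag, to 13 of 14 (20 of 21) with no lag. At Months 1 and 2 it ranges from none to 23 of 28 (36 of 42) visits. These ranges rest on even entry over 1 to 12 months and nominal visit days. They count contacts made after the first code is known; they do not estimate bias, which arises only if the knowledge changes conduct. To conclude that the blind on the itch diary is broken, or that the itch result is biased, would go beyond the documents.

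One uncertainty affects the remedy. Section 7 reports a non-significant trend in daily itch scores for 5 mg against placebo over a two-month active period. Its source is not named. The drug, dose, measure and duration match this trial, whereas the earlier chronic pruritus trial in section 6 lasted 6 weeks and used a visual analogue scale. If the trend comes from this trial, an arm comparison has already been seen. The judgement rests on the supplied text; removed title, signature, contact and consent pages are not counted as gaps.

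**What to change.** **Main change.** Keep individual disclosure to subjects if it is wanted, and add the following to section 8:

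- One existing person with no assessment or analysis role, for example whoever already holds the randomisation list, holds the codes.
- That person breaks a subject's code only after the subject's Month 3 survey is done and the diary has been received, and alone makes the arm-specific contacts.
- The survey interviewer, AE assessor, photograph reader and analyst stay blinded, except in a medical emergency, until the last Month 3 contact is complete, photographs are read, the between-arm analysis is fixed in writing and the database is locked.

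**Cost.** A few sentences of protocol text, a little more administration and a short written analysis. Sample size, alpha and power do not change. Some leakage remains, because subjects may tell staff their arm during extension calls.

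**Optional stronger version.** Send one uniform extension invitation to every completer and keep codes concealed until lock. The extension is already offered to all completers, so nobody need wait longer for it. The downside is that subjects, including adolescents, decide without knowing their first-phase arm. Early completers learn it later, by roughly the entry spread plus the time to lock. The wording that distinguishes continuing from repeating would also go, and staff following extension subjects would not know their earlier exposure.

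**If the section 7 trend is from this trial.** Say so, apply the blinding to the assessments that remain, and label any between-arm analysis fixed afterwards as post hoc.

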6. Have chronic liver disease, ie, AST or ALT greater than 2 times the upper limit of normal. Subjects with hepatitis B and C who have normal liver function may be enrolled.
7. Have a current malignancy (such as Hodgkin's lymphoma, B or T cell lymphoma, or myeloma) or blood cell dyscrasia (eg, polycythemia or myelofibrosis) that would lead to systemic chronic pruritus.
8. Subjects with untreated hyperthyroidism.
9. Have pruritus of psychogenic etiology (delusions of parasitosis, obsessive compulsive disorder and major depression) or neuropathic etiology (due to shingles, spinal cord injury or with neurologic deficit).
10. Have pruritus due to urticaria, drug allergy, or infection (such as pityriasis rosea or tinea or active human immunodeficiency virus [HIV]). Note: Subjects with HIV who have undetectable viral load, CD 4 counts >200 cells/cc, and stable retroviral therapy may enroll.
11. Have taken investigational medications within 30 days prior to Screening.
12. Are unwilling to discontinue specific pruritus medications for at least two weeks prior to initiation of study and throughout the study period (all severe CYP34A inhibitors - this

- includes **miconazole**, **delavirdine**, conivaptan, Clarithromycin, telithromycin, nefazodone, itraconazole, ketoconazole, indinavir, lopinavir, nelfinavir, **ritonavir**, saquinavir).
13. Within in the past 12 months, have expressed suicidal ideation with some intent to act.
 14. Started or changed medications, creams, or emollients including over-the-counter (OTC) preparations or bath oil treatment for relief of pruritus within 3 months prior to Screening.
 15. Have any social or medical condition (e.g. alcoholism, drug dependency, psychotic state) that, in the investigator's opinion, might interfere with the subject's ability to comply with the requirements of the protocol.

Statistical basis for the number of subjects to be enrolled:

This 14 patient clinical trial is powered only to determine large differences in the placebo (N=7) vs. 5 mg (N=14) groups. In power calculations, we assumed a mean of 8 NRS for the placebo vs. 5 NRS for the active with a SD of 3, and p-value of 0.05 (one sided).

| Two-sample t test with equal variances | | | | | |
|--|-----|------------------------|-----------|-------------------------|----------------------|
| | Obs | Mean | Std. Err. | Std. Dev. | [95% Conf. Interval] |
| x | 14 | 5 | 0.8017837 | 3 | 3.267852 6.732148 |
| y | 7 | 8 | 1.133893 | 3 | 5.225463 10.77454 |

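### The sizing table uses 21 independent observations in a trial described as 14 patients; the counts must be reconciled, and the plan should say that only randomised, blinded records enter the efficacy comparison.

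*Combined protocol and SAP*

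**What the plan says.** Three places in section 8 of the combined protocol and SAP bear on this.

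- *Statistical basis for the number of subjects*: "This 14 patient clinical trial is powered only to determine large differences in the placebo (N=7) vs. 5 mg (N=14) groups". For the inputs, "we assumed a mean of 8 NRS for the placebo vs. 5 NRS for the active", with SD 3 and a one-sided 0.05 level. The table below it is an equal-variance two-sample t test with 14 and 7 observations, 21 combined and 19 degrees of freedom: t = -2.1602, one-sided p = 0.0219. Neither a power figure nor an allocation ratio is given.
- *Statistical plan for the primary hypothesis*: "For each dosage group, we will use linear regression methods with mix effects", following change in itch from baseline. No analysis set, study period or data cut is named.
- *Text after the Schedule of Events*: each subject is unblinded individually after 3 months, and completers are offered 2 months of active drug. Former placebo subjects are "asked if they would like to repeat the study on open label for 2 months". They receive a daily diary and are contacted by phone at baseline and at months 1, 2 and 3.

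**The concern.** The three counts (14 in total, 7 on placebo, 14 on 5 mg) cannot all describe separate people. The table takes the two group sizes at face value, so its standard error, degrees of freedom and p value belong to a 21-person trial. If 14 people are randomised, the stated precision is too good. The plan says that this study will supply the effect size and SD for sizing a larger trial, so readers need to know how many independent subjects lie behind those estimates.

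A related gap is that the plan does not say which records form a dosage group. A former placebo subject who takes active drug in the extension could be read as belonging to both groups. Itch is self-reported, and scores given in the knowledge of taking active drug are not comparable with blinded placebo scores.

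**Working it through.** **Inputs.** From the sizing section: means 5 and 8 (difference 3), SD 3, one-sided 0.05, group sizes 14 and 7, total 14. Assumed, because the plan does not state them: the allocation ratio if there are 14 patients (7:7 as the base case, 10:4 to 7:7 as the range) and no dropout.

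**1. The plan's own table.** SE = 3 × √(1/14 + 1/7) = 1.3887. Then t = -3 / 1.3887 = -2.160 on 14 + 7 - 2 = 19 df, with one-sided p = 0.0219 and two-sided p = 0.0437. The combined mean is (14 × 5 + 7 × 8) / 21 = 6. All of these match the printed values, so the table is correct for 21 independent subjects.

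**2. The counts.** If the total is 14, the overlap between the groups is 7 + 14 - 14 = 7. All three counts hold together only if every placebo subject is also in the 5 mg group. The 21 observations would then come from 14 people, which an independent-samples test with 19 df does not allow for. Otherwise at least one count is wrong.

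**3. Unique subjects only.** SE = 3 × √(1/n₁ + 1/n₂). Power is the probability that a noncentral t, with n₁ + n₂ - 2 df and noncentrality 3/SE, exceeds the one-sided 5% critical value.

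| Active : placebo | SE | df | t | One-sided p | Power for 3 points |
|---|---|---|---|---|---|
| 14 : 7 (as printed) | 1.389 | 19 | -2.160 | 0.0219 | 66.9% |
| 7 : 7 | 1.604 | 12 | -1.871 | 0.0430 | 54.7% |
| 9 : 5 | 1.673 | 12 | -1.793 | 0.0491 | 51.8% |
| 10 : 4 | 1.775 | 12 | -1.690 | 0.0584 | 48.0% |

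At 7:7 the standard error is 1.604 / 1.389 = 1.15 times the printed one. At 10:4 the assumed 3-point difference would no longer reach one-sided 0.05. If the true enrolment is 21 at 2:1, the first row stands and only the total of 14 needs correcting.

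**4. What pooling would do, if it happened (hypothetical).** Take 7 randomised active subjects plus 7 open-label repeats against the same 7 on placebo. Assume that all 7 placebo subjects enter the extension, and that the repeats score s points lower because of open-label knowledge or time.

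- The shift in the estimated difference is (7 × 0 + 7 × s) / 14 = s/2. That is 0.5 point for s = 1 and 1.0 point for s = 2, towards drug.
- One-sided rejection with no drug effect was simulated with the pooled t test at nominal 5%, over within-subject correlation 0 to 0.7 (100,000 runs per setting). It is 4.7% to 9.5% for s = 1, 10.7% to 15.4% for s = 2, and 1.3% to 5.0% for s = 0. Repeat runs move these by up to about 0.3 percentage points, so the range for 1 to 2 points is about 5% to 16%.

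**The case against.** A reader might infer from the matching arithmetic that the plan intends to count the 7 placebo subjects twice and to place their open-label scores in the 5 mg arm. The documents do not support that.

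- No sentence says that extension records join the efficacy comparison.
- The extension is offered to those who have completed the study, is named as a separate portion distinct from the first phase, and has its own follow-up schedule.
- The preliminary data in section 7 describe the comparison with placebo over the two-month active trial period and mention no extension data.
- The extension is optional. Sizing on double counting would mean assuming that every placebo subject completes and accepts. Grouping by dose would also bring in the extension records of former active subjects, which the count of 14 does not reflect.
- A wrong total is at least as simple an explanation, since 21 patients at 2:1 fits the whole printed table.
- The error rates come from a t test on one score per record. The planned analysis is a mixed-effects regression, in which a subject effect could absorb at least part of the within-subject correlation. It would not remove an open-label shift.

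All of this stands, and the blinded period is the ordinary reading. Two things survive it. The counts still conflict whichever explanation is right. And descriptive labels are not an analysis rule: the planned time points of 1, 2 and 3 months do not exclude repeat records, because the extension uses the same months.

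It can also be said that the trial claims power only for large differences. That is fair, but the stated precision should still match the number of people randomised.

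**Conclusion.** The sizing is internally inconsistent as written. For 14 unique patients at an assumed 7:7, the assumed 3-point difference has about 55% power (48% to 55% for splits from 10:4 to 7:7), against 67% for the 14 v 7 on which the table rests. If enrolment is really 21 at 2:1, the table is right and the stated total is wrong. The documents do not settle which.

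The missing rule on extension records is a secondary gap, not evidence of planned pooling. The bias of 0.5 to 1.0 point and the error of about 5% to 16% are conditional on pooling, full extension uptake, an assumed shift of 1 to 2 points, correlation 0 to 0.7 and a simple t test. With no shift the error is at or below nominal. That the extension dose is 5 mg is itself inferred, since the text says only active drug.

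**What to change.** 1. Reconcile 14, 7, 14 and 21, and state the number randomised and the allocation ratio.
2. Rebuild the sizing table on unique randomised subjects and state the power. If there are 14 at 7:7, it becomes SE 1.60, df 12, one-sided p 0.043 and power about 55% for 3 points. If there are 21 at 2:1, keep the table, correct the total and give the power as 67%.
3. Add to the statistical plan: *The efficacy comparison uses only records from the randomised double-blind period, with each subject counted once in the arm assigned. Data from the open-label extension are summarised separately and are not added to either arm.*

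The cost is one corrected paragraph and table plus two sentences. The downside is a slightly less favourable stated precision if 14 is the true enrolment. No change to visits or data collection is needed.
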